The number and percent of participants with peri-infusion grade 1-4 AEs will be summarized by day and grade, and by type and grade. The percentage of participants with AEs will be compared between treatment groups according to grade cut-offs, e.g., “percent of participants with any AE”, “percent of participants with grade 2 or higher AEs”, etc., using CMH tests. The total number of events and median (IQR) number of events per participant will also be summarized.

Additionally, the incidence of grade 3 and higher AEs will be summarized (number and percent of participants) by MedDRA® System Organ Class and grade using stratified CMH tests. Incidence of grade 3 and 4 AEs will also be compared between treatment groups as part of composite safety endpoints using time-to-event methods.

Significance level, two-sided tests: Unless noted otherwise, statistical tests and confidence intervals will be 2-sided, confidence intervals will have approximate 95% coverage probability, and test results with P-values ≤ 0.05 will be considered “significant”.

Cut-date for interim reviews: Analysis data sets will be locked several days (or weeks) prior to the review date, to allow the unblinded statisticians time to prepare a consistent report.

¹ The Medical Dictionary for Regulatory Activities terminology is the international medical terminology developed under the auspices of the International Conference on Harmonization of Technical Requirements for Registration of Pharmaceuticals for Human Use (ICH). MedDRA® is a registered trademark of the International Federation of Pharmaceutical Manufacturers and Associations (IFPMA)

The cut-date may be earlier than the date of the data lock, to allow for lag time in the reporting of events. Early in the trial, the cut date and lock date will be very close to the review date, to ensure timely safety reviews.

4 Enrollment and Eligibility

For the open report, the following enrollment and eligibility summaries will be provided:

- Enrollment over calendar time: plot by day or week, cumulative and increments.
- Enrollment by study design stratum (4 strata), and pooled across the relevant design strata for the aviptadil/placebo and remdesivir/placebo comparisons.
- Enrollment by site pharmacy and by country: number (%)
- Eligibility: number (%) and reasons for eligibility violations

These summaries will be provided overall, and by disease severity randomization stratum.

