The primary safety outcome of *grade 3 or 4 AEs, SAEs, PSESEs, or death through Day 5* includes potentially infusion-related outcomes; the analysis of the primary safety outcome is described in section 7. The current section describes safety analyses that are focused on the peri-infusion time period (i.e., during and within 2 hours after the infusion).

Peri-infusion signs and symptoms are reported as AEs (with grade and action taken) on eCRFs. Local labs are reported at baseline, Days 1 and 2 for all participants, and Days 3 and 5 if clinically available. Labs on Day 5 are reported for participants who are treated in the ICU.

Side effects of aviptadil observed in previous studies include:

- Hypotension with and without vasopressor
- Diarrhea
- Facial flushing
- Bradycardia
- Tachycardia

For the aviptadil versus placebo comparisons, incidence and management of hypotension in particular will be monitored in detail. Blood pressure is recorded prior to the start of the infusion and every 2 hours peri-infusion on each infusion day. Vasopressor use and dose are reported: prior to the start of the infusion, the highest dose peri-infusion, and the dose at 2 hours after the infusion.

The following data summaries will be provided overall for Days 0-2, and separately by day. Treatment groups will be compared using statistical methods described under “analysis principles” in section 3; comparisons will be stratified by disease severity at study entry (2 categories, by use of *invasive mechanical ventilation or ECMO*).

- Number and percentage of participants with infusion-related signs or symptoms (reported during the infusion or within 2 hours after the infusion), by type and grade, by type and grade cut-off (i.e., \geq grade 2, \geq grade 3, etc.), and by type and action taken.

Comments:

1. For aviptadil, **diarrhea is not included in the composite safety outcome** of incident grade 3 or 4 AEs, SAEs, PSESEs or death unless it is a SAE or leads to discontinuation of the infusion (for the day, or permanent discontinuation). Therefore, peri-infusion diarrhea AEs will be summarized in two ways: (1) as reported, and (2) restricted to diarrhea AEs that lead to discontinuation of the investigational agent.
2. Hypotension, diarrhea, facial flushing, bradycardia, and tachycardia are collected as part of the infusion-related signs and symptoms, and will be summarized by type and grade, and by type and action taken in response to the AE, as described above.

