- All-cause mortality through follow-up will be analyzed using time-to-event methods. Cumulative proportions of participants who died in each treatment group will be estimated using Kaplan-Meier estimates, and summarized in tables (proportion of participants who died by Days 5, 14, 28, 60, 90, month 6) and figures (Kaplan-Meier curves with pointwise 95% CIs). Treatment groups will be compared for time to death using log-rank tests,

stratified by disease severity at study entry, and HRs will be estimated with 95% CIs using stratified Cox proportional hazards models.

- Cause of death will be MedDRA® coded and summarized by treatment group.
- The following composite endpoints will be analyzed using time-to-event methods (cumulative proportions of participants with events will be estimated using Kaplan-Meier curves with pointwise 95% CIs; treatment groups will be compared using log-rank tests; numbers and percent of participants with events will be summarized by treatment group, and overall HRs with 95% CI will be estimated using Cox proportional hazards models):
 - Composite of incident grade 3 or 4 clinical adverse events, SAEs, PSESEs, or death through Day 28
 - Components of the composite endpoint will be also be summarized.
 - In addition to time-to-event analyses, the treatment groups will be compared for the proportion of participants who experienced the composite endpoint by Day 28 using a stratified CMH test, similar to the primary safety analysis on Day 5.
 - Composite of SAEs, PSESEs, or death through Day 28 and Day 90
 - Composite of hospital re-admission or death through Day 90 and Month 6.
- Grade 3 or 4 AEs, SAEs, and UPs will be classified by MedDRA® system organ class. AEs will be graded for severity according to the *DAIDS AE Grading Table*, except for peri-infusion hypotension AEs, which are graded according to Table D-3 in [Appendix D](#).
- Incident **grade 3 and 4 clinical AEs** are reported through Day 28. (A grade 3 or 4 AE is considered “incident” if the event was not present at baseline or increased to grade 3 or 4 from grades 1 or 2, or increased to grade 4 from grade 3.)
 - AEs that were reported to have occurred on Day 0 prior to the first infusion will be considered “baseline” and thus will be excluded from the analysis of incident AEs.

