 - Grade 3 and 4 AEs that occur peri-infusion (i.e., during and within 2 hours after the infusion) on Days 0-2 and are reported on the infusion eCRFs will be included as incident grade 3 or 4 AEs, unless noted otherwise.
 - The number and percent of participants with incident grade 3 and 4 AEs will be summarized by MedDRA® system organ class and grade, and by MedDRA® system organ class and grade cut-off (i.e., grade ≥ 3 , grade 4). Comparisons between treatment groups will be for the proportion of participants who experienced AEs of grade 3 or higher through Day 28, using stratified CMH tests or logistic regression, stratified by disease severity at study entry (*invasive mechanical ventilation or ECMO* vs. neither). Treatment groups will be compared for incidence of grade 3 or 4 AEs overall, and by system organ class.
 - System organ classes may be split up into MedDRA® preferred terms (PT) for the most frequent system organ classes, particularly for classes where the treatment difference is significant.
 - Other clinically meaningful AE groupings (beyond system organ class) may be developed by the study team, who are blinded to the treatment effect.
- Grade 1-4 clinical AEs are reported at baseline (Day 0 prior to infusion of the investigational agent), on Days 0-2 peri-infusion (during and within 2 hours after the

infusion), as well as on Days 14 and 28. The peri-infusion AEs are collected as “signs and symptoms” via checklist on the infusion eCRFs.

The analysis of peri-infusion AEs is described in section 6. In particular, the number and percent of participants with peri-infusion AEs will be summarized by day and grade, by type and grade, and by type and action taken (i.e., modification or discontinuation of the infusion).

- Treatment groups will be compared for the proportion of participants who developed **PSESEs** through Day 28 and through Day 90, using stratified CMH tests. In addition to the overall comparison, individual components of the composite PSESE outcome will be tabulated, and compared between treatment groups using stratified CMH tests. The components of the PSESE outcome are listed in [Appendix C](#).

Comment: The composite outcome of *clinical organ failure, serious infections, or death* is identical to the composite of all PSESEs; individual components of clinical organ failure are listed in [Appendix B](#).

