Appendix D. Safety Data Collection

Table D-1. Overview of Safety Data Collection (protocol version 2.0, section 10).

	During and at least 2 hrs after infusion (all days on which infusion occurs)	Day 0–7	Day 14	Day 28	Day 90
Infusion-related reactions and symptoms of any grade ^a	X				
All grade 3 and 4 clinical AEs (new or increased in severity to Grade 3/4)	X	X	X ^b	X ^b	
Protocol-specified exempt serious events (PSESEs) ^c	Collected through Day 90				
SAEs that are not PSESEs	Collected through Day 90				
Unanticipated problems	Collected through End of Subject Participation (Day 180)				
Hospital admissions and deaths	Collected through End of Subject Participation (Day 180)				
Any SAE related ^d to study intervention	Collected through End of Subject Participation (Day 180)				

^a This includes reporting of AEs of any grade present on day 0, before the first infusion. This allows assessment of whether a given AE is new after infusion.

^b Participants will be asked about all new relevant adverse events of Grade 3 or 4 which have occurred since the last data collection, up to that time point. On these visits, AEs of Grade 1 or 2 that are present on the day of the visit will also be collected.

^c These are explained and defined in section 10.2.3 of the protocol, and [Appendix B](#) of this SAP.

^d Relatedness determined as per protocol rules in protocol section 10.1.5.

Table D-2. Overview of Safety Data Collection for Remdesivir (stratum 3) (protocol version 2.0, Appendix H2, Table 1).

	Day 0–7	Day 14	Day 28	Day 90
All grade 3 and 4 clinical AEs (new or increased in severity to Grade 3/4)	X	X ^a	X ^a	
Protocol-specified exempt serious events (PSESEs) ^b	Collected through Day 90			
SAEs that are not PSESEs	Collected through Day 90			
Unanticipated problems	Collected through End of Subject Participation (Day 180)			
Hospital admissions and deaths	Collected through End of Subject Participation (Day 180)			
Any SAEs related ^c to study intervention	Collected through End of Subject Participation (Day 180)			

^a Participants will be asked about all new relevant adverse events which have occurred since the last data collection, up to that time point. On these visits, AEs of Grade 1 or 2 that are present on the day of the visit will also be collected.

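### The SAP compares peri-infusion signs and symptoms between arms by timing alone and does not use the Day 0 pre-infusion record, which can weaken the contrast for low-grade aviptadil reactions

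*SAP*

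**What the plan says.** **What is compared.** SAP section 6.1, under Safety, lists "Number and percentage of participants with infusion-related signs or symptoms (reported during the infusion or within 2 hours after the infusion"). Within each type of event, the tables break this down by grade, grade cut-off and action taken. Arms are compared with the section 3 methods. In the adverse-event paragraphs of section 3: "The number and percent of participants with peri-infusion grade 1-4 AEs will be summarized by day and grade, and by type and grade". The next sentence there adds: "The percentage of participants with AEs will be compared between treatment groups according to grade cut-offs", with any AE and grade 2 or higher as examples, using CMH tests. Neither place says how to treat a symptom that was there before the first infusion.

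**What is collected.** Section 7.1 states: "Grade 1-4 clinical AEs are reported at baseline (Day 0 prior to infusion of the investigational agent"), as well as peri-infusion on Days 0-2 by checklist. It then refers the analysis of peri-infusion AEs back to section 6. Appendix D, Table D-1, footnote a gives the purpose of the Day 0 record: "This allows assessment of whether a given AE is new after infusion".

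**Where a baseline rule exists.** In section 7.1 a grade 3 or 4 AE is incident "if the event was not present at baseline or increased to grade 3 or 4 from grades 1 or 2", or rose from grade 3 to grade 4. Events on Day 0 before the first infusion count as baseline and "thus will be excluded from the analysis of incident AEs". Both statements sit under incident grade 3 and 4 clinical AEs. The same list brings in "Grade 3 and 4 AEs that occur peri-infusion (i.e., during and within 2 hours after the infusion) on Days 0-2" that are reported on the infusion forms, unless noted otherwise.

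**The concern.** The SAP records a pre-infusion baseline for a stated purpose, but no grade 1-2 analysis serves that purpose. Two of the five aviptadil side effects listed in section 6.1 are hypotension and tachycardia. All participants have critical respiratory failure, and section 5 plans baseline tables of heart rate of 100 or more, low blood pressure and vasopressor use. Some participants may therefore have these signs before any study drug is given.

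If such a sign persists unchanged and is ticked on the infusion checklist, it counts as infusion-related in either arm. What is at stake is the ability to see a real excess of low-grade reactions to an agent that section 7.2 describes as having limited safety data. Peri-infusion grade 1-4 AEs are also part of the weekly closed safety report (section 2).

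**Working it through.** The SAP gives no symptom rates, pre-infusion prevalence or power for this comparison, so there is no figure to reproduce. The check is of direction and possible size.

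**Inputs from the SAP:** 320 per group (section 1.4); two-sided 5% tests (section 3).

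**Assumed inputs:** *b*, the proportion with the symptom before the first infusion, equal in the two arms by randomization and persisting into the infusion window; *r*, the new-onset rate among those free of it, 10% on placebo and 20% on aviptadil.

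**Formulas**
- As-reported rate: b + (1 - b)r. This exceeds r by b(1 - r), so both arms rise.
- As-reported risk difference: (1 - b)(r1 - r0), so the contrast shrinks by the factor (1 - b).
- If r1 = r0, the two as-reported rates are equal: no bias under the null.
- Power: unstratified two-proportion z-test, pooled variance under the null.

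**Worked case, b = 30%**
- Placebo: 0.30 + 0.70 × 0.10 = 37.0%. Aviptadil: 0.30 + 0.70 × 0.20 = 44.0%.
- Difference: 7.0 points. OR = (0.44/0.56)/(0.37/0.63) = 1.34. Power 43.8%.
- Symptom-free participants only: 320 × 0.70 = 224 per arm, 10% versus 20%, OR 2.25, power 84.5%.
- New events over all 320 per arm: 7% versus 14%, power 82.5%.

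| b | As reported | OR | Power, as reported | Power, symptom-free only | Power, new events over all 320 |
|---|---|---|---|---|---|
| 0% | 10.0% vs 20.0% | 2.25 | 94.5% | 94.5% | 94.5% |
| 5% | 14.5% vs 24.0% | 1.86 | 86.3% | 93.4% | 93.2% |
| 10% | 19.0% vs 28.0% | 1.66 | 76.7% | 92.1% | 91.7% |
| 20% | 28.0% vs 36.0% | 1.45 | 58.3% | 88.9% | 87.8% |
| 30% | 37.0% vs 44.0% | 1.34 | 43.8% | 84.5% | 82.5% |

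**Other assumed onset rates, b from 5% to 30%**
- 5% vs 12%: power as reported falls from 70.5% to 25.2%; among the symptom-free, from 87.4% to 75.9%.
- 20% vs 30%: as reported from 75.8% to 42.6%; among the symptom-free, from 81.4% to 68.7%.

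The choice between the last two denominators matters little. What costs power is counting unchanged pre-existing symptoms. For a cut-off such as grade 2 or higher, b is the prevalence at or above that grade. The model has no worsening among those already symptomatic, which a new-or-worsened count would also pick up.

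**The case against.** **The SAP is silent; it does not say that pre-existing symptoms are kept.** A reader might infer that it deliberately retains them, since section 6.1 speaks of an as-reported summary. That wording concerns only the two ways of summarising diarrhea, and footnote a points the other way. Whether an unchanged symptom is entered on the infusion checklist at all depends on form instructions that the SAP does not reproduce. This stands, and it makes the effect conditional. It does not remove the gap, because sections 3 and 6.1 as written contain no step that uses the Day 0 record.

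**Much of the safety review is already protected.** This also stands. Grade 3/4 events have the incident definition and the Day 0 exclusion in section 7.1. For hypotension, section 6.1 refers MAP falls and vasopressor increases to the daily pre-infusion value and separates participants by vasopressor use before the Day 0 infusion. Heart-rate trajectories, tables by action taken, and infusion reductions or discontinuations due to AEs do not depend on mere presence of a symptom. The DSMB judges the totality of evidence and may ask for more (section 10.1). The remaining gap is the graded checklist, including the hypotension AE line by grade.

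**The size is assumed, and no power target applies to these tables.** Correct. At 5% prevalence the loss is modest (86.3% against 93.4%).

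**A fixed Day 0 reference has its own blind spot.** A symptom present on Day 0 that resolves and returns at the same grade during a later infusion would not count as new or worsened. This is a good reason to keep the as-reported comparison rather than replace it.

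**Conclusion.** The point holds for the comparisons of checklist signs and symptoms in sections 3 and 6.1: any grade, grade 2 or higher, and by type. The definition rests on timing alone, and the Day 0 record collected to judge newness enters none of them. If pre-existing symptoms are entered on the infusion checklist, the contrast moves toward no difference. In the main illustration the OR falls from 2.25 to between 1.86 and 1.34, and power from 94.5% to between 86.3% and 43.8%, as prevalence runs from 5% to 30%. These figures rest on assumed onset rates, equal prevalence in the arms and full persistence into the infusion window.

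Three stronger readings are not supported:
- That aviptadil reaction rates would be understated. They would be raised, as would the placebo rates; only the contrast is diluted.
- That the test would be biased. With equal prevalence there is no bias under the null.
- That the primary safety outcome is compromised or reactions in general are hidden from the DSMB. The incident grade 3/4 analyses, the Day 5 composite, and the MAP and vasopressor summaries do not rest on this count.

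**What to change.** In sections 3 and 6.1, add a tested comparison of peri-infusion signs and symptoms that were absent, or of lower grade, on the Day 0 record taken before the first infusion. Give it by type, by grade cut-off and for any AE. Report it beside the as-reported comparison, which stays in the plan and stays tested. State the denominator.

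The cost is one extra set of tables and a merge with the Day 0 AE record. No new data are needed. The small downside is that a symptom which resolves and recurs at its Day 0 grade appears only in the as-reported version, so the two should be read together.

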6.1 Infusion of Aviptadil (Active or Placebo)

Study population (Aviptadil cohort, mITT): Unless otherwise noted, the study population consists of participants who were randomized to aviptadil or its placebo, excluding those who did not receive **any** aviptadil/placebo (modified intention-to-treat [mITT]).

Aviptadil (and its placebo) will be administered by intravenous infusion for 3 days, over a continuous 12 hour period each day. The protocol-specified infusion rate for the first infusion day is 50 pmol/kg/hr (Day 0), to be increased to 100 pmol/kg/hr on Day 1 and 150 pmol/kg/hr on Day 2. This corresponds to a protocol-specified dose of 600, 1200, or 1800 pmol/kg for infusions on Days 0-2. Infusions may be paused or discontinued due to side effects, or the target dose may be decreased.

In the following, “aviptadil” refers to the blinded aviptadil infusion (active or placebo). “Peri-infusion” refers to the time period during or within 2 hours after the infusion.

The following statistics will be used to summarize the infusions in each treatment group (active and placebo) for the closed reports, or pooled across treatment groups for open reports shared with investigators. For the closed report, treatment groups will be compared for the various outcomes using methods described in section 3.

For all participants who were randomized (**Aviptadil ITT cohort**):

- Non-administration of aviptadil:
Number and percentage of participants who did not receive any aviptadil, and reasons

All other analyses will use the **Aviptadil mITT** cohort (i.e., analyses will exclude those who did not receive any blinded aviptadil in the study).

- For each of the Days 0-2: number and percentage of participants who did not receive any aviptadil, and reasons
- Adherence to the study treatment on Days 0-2 will be summarized over time: percent of participants who received no infusion, some (<50% of the day's protocol-specified infusion dose), most (50-90%) and full infusion (>90%) for each of the three days, and overall.
 - For each day, for each participant, the "percent dose infused" will be the estimated dose delivered expressed as percentage of the protocol-specified dose for the day (600, 1200, or 1800 pmol/kg).
 - For the summary across Days 0-2 ("overall"), categories are formed by the average of the three daily percent doses infused.

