- **Peri-infusion hypotension summary**

- Peri-infusion hypotension AEs reported on infusion eCRF (by grade: highest grade on Days 0-2, or highest grade on the day for the day-specific summaries)
- Blood pressure (across days 0-2, and on each day)

- MAP decrease by > 20 mmHg from daily pre-infusion baseline
- Lowest peri-infusion MAP (mean [SD] across participants)
- Incidence of MAP < 65 mmHg (compared to daily pre-infusion baseline)
- Percentage of peri-infusion BP data points with MAP <65 mmHg (mean [SD] of percentage across participants)
- Infusion modifications for hypotension (prevalence on ≥ 1 day)
 - Infusion not attempted for hypotension/vasopressor use
 - For those with any infusion modification, summary of the highest-intensity infusion modification (across Days 0-2, and for each day): Rate decreased but infusion not paused; infusion paused but resumed; infusion discontinued for the day; infusion discontinued permanently
- Vasopressor use peri-infusion
 - New peri-infusion vasopressor use on any day among patients not receiving vasopressors pre-infusion on Day 0 (Number in subgroup, N, %)
 - New or increased peri-infusion vasopressor use on any day among patients who received vasopressors pre-infusion on Day 0 (Number in subgroup, N, %)
 - Maximum peri-infusion vasopressor rate increase within a study day from pre-infusion to peak (in NE units; max over Days 0-2, then mean across patients; 0 NE is imputed for time points when no vasopressor is used. If the maximal peri-infusion vasopressor dose is lower than the pre-infusion dose, then 0 NE will be imputed).
 - Percent with vasopressor rate higher at 2 hours post infusion than pre-infusion
 - Incidence of vasopressor rate increase by > 0.03 mcg/kg/min NE units peri-infusion relative to daily pre-infusion baseline (N, %)
 - Incidence of peak (absolute) vasopressor rate of > 0.1 mcg/kg/min NE units
- IV fluid use peri-infusion in response to hypotension AE
 - IV fluid (crystalloid ≥ 500 mL or equivalent colloid volume) peri-infusion, prevalence
 - For those who received IV fluid or colloid: maximum IV fluid volume on one day (max across days for each participant, then mean across participants)
- Summary of *SBP and MAP trajectories*, from infusion start to 2 hours after infusion
 - Mean trajectories will be plotted by treatment group, and compared using longitudinal models.

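### Two aviptadil hypotension comparisons are confined to subsets formed after randomization, and no all-mITT version of either is specified

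*SAP*

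**What the plan says.** SAP section 6.1 fixes the analysis set for the infusion summaries: "All other analyses will use the Aviptadil mITT cohort", that is, everyone randomized to aviptadil or its placebo who received some of it. Under Safety in the same section, two sentences introduce the hypotension list: "The following data summaries will be provided overall for Days 0-2, and separately by day" and "Treatment groups will be compared using statistical methods described under “analysis principles” in section 3". The comparisons are stratified by disease severity. No item in the list is marked as descriptive only.

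Two items narrow the denominator to people who have already had an event:

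- "For those with any infusion modification, summary of the highest-intensity infusion modification (across Days 0-2, and for each day", running from a rate decrease up to permanent discontinuation;
- "For those who received IV fluid or colloid: maximum IV fluid volume on one day", taken as the largest day per participant and then averaged.

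The maximum vasopressor rise, in the same list, does not narrow it: "0 NE is imputed for time points when no vasopressor is used".

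The change measures use the same-day pre-infusion value as reference, for example "MAP decrease by > 20 mmHg from daily pre-infusion baseline" and "Incidence of vasopressor rate increase by > 0.03 mcg/kg/min NE units peri-infusion relative to daily pre-infusion baseline". The maximum vasopressor rise is also taken within a study day. The planned infusion rate goes from 50 to 100 to 150 pmol/kg/hr over Days 0, 1 and 2.

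**The concern.** Having the infusion modified, or being given fluid, happens after randomization and is something aviptadil may cause. Participants who enter these subsets on aviptadil may differ from those who enter on placebo. If aviptadil adds many mild reactions, they enlarge its subset and dilute the severe share, and the recipient-only mean fluid volume can fall for the same reason. A test run inside the subset could then favour the arm with more toxicity.

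The SAP singles out hypotension for detailed monitoring in the aviptadil comparison (section 6.1) and describes existing aviptadil safety data as limited (section 7.2). A compared item in a closed report that can carry the wrong sign is worth correcting.

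A second, smaller matter is the daily reference. On Days 1 and 2 it is measured after earlier infusions, so any effect still present at that time is subtracted out. The size of a change built up over several days is then not recorded by these items.

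**Working it through.** The SAP states no hypotension, modification or fluid rates, so there is no planned figure to reproduce. All rates, volumes, SDs and carry-over fractions below are assumptions chosen to show direction.

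**1. Modification intensity among those modified.** Let m be the proportion with any modification for hypotension and s the proportion discontinued, both over all mITT. The subset comparison sees s/m. It favours aviptadil when s_A/m_A < s_P/m_P, which is the same as m_A/m_P > s_A/s_P: the ratio of any-modification rates exceeds the ratio of severe rates.

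| Any modification, A vs P | Discontinued, all mITT | Discontinued among modified | Subset result |
|---|---|---|---|
| 40% vs 10% | 8% vs 4% | 20% vs 40% | reversed |
| 20% vs 10% | 6% vs 4% | 30% vs 40% | reversed |
| 20% vs 10% | 8% vs 4% | 40% vs 40% | difference hidden |
| 40% vs 10% | 20% vs 4% | 50% vs 40% | direction kept |

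In row 1 the odds ratio for discontinuation is (0.08/0.92)/(0.04/0.96) = 2.09 over all mITT and (0.20/0.80)/(0.40/0.60) = 0.38 within the subset.

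**2. Fluid volume among recipients.** Assume 30% of the aviptadil arm receive a mean of 750 mL and 10% of the placebo arm a mean of 1000 mL. Recipients: 750 vs 1000 mL, lower on aviptadil. Over all mITT with 0 mL for the rest: 0.30 × 750 = 225 mL vs 0.10 × 1000 = 100 mL, higher on aviptadil.

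**3. Daily versus Day 0 reference, MAP fall above 20 mmHg.** Assume the daily fall to nadir is normal with mean 8 and SD 8 mmHg on placebo, and that aviptadil adds 5 mmHg on each day. A fraction of each day's added fall persists into the next pre-infusion value.

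- Same-day reference: placebo P(Z > (20 − 8)/8) = P(Z > 1.5) = 7% per day. Aviptadil P(Z > (20 − 13)/8) = P(Z > 0.875) = 19% per day, whatever the carry-over.
- Any day of three: 1 − 0.933³ = 19% on placebo and 1 − 0.809³ = 47% on aviptadil.
- Day 0 reference on Day 2, 50% carry-over: mean fall 13 + 5 = 18, so P(Z > 0.25) = 40%. With 100% carry-over: mean fall 13 + 10 = 23, so P(Z > −0.375) = 65%.
- Any day with the Day 0 reference (simulation of 200,000 participants per scenario): 47%, 66% and 83% on aviptadil at 0, 50 and 100% carry-over, against 19% on placebo.
- Front-loaded case (10 mmHg added on Day 0 only, fully persisting): on Days 1 and 2 the daily reference shows 7% in both arms, and the Day 0 reference shows 40% on aviptadil. The any-day daily figure is still 48% vs 19%.

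The daily reference therefore attenuates or hides later-day differences. It does not reverse the overall one.

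**4. One participant's vasopressor rate.** Suppose it goes 0 to 0.03, 0.03 to 0.06 and 0.06 to 0.09 mcg/kg/min NE over the three days. No day exceeds 0.03. The within-day maximum rise is 0.03, while the rise from Day 0 is 0.09, three times the threshold. The 0.09 peak is also below the absolute cut-off of 0.1.

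**The case against.** A reader might infer that hypotension severity is compared only among people who already had a reaction. The SAP does not support that:

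- Sections 6.1 and 7.1 plan an all-mITT table of peri-infusion symptoms, naming hypotension, by what was done to the infusion.
- Highest hypotension grade over Days 0-2 is compared, and Table D-3 in Appendix D grades hypotension partly by infusion response.
- Section 6.1 has an all-mITT worst-category table for infusion-rate decreases, with a no-decrease level.
- Both subset lines sit with a prevalence. From row 1 above, a reader can multiply 40% by 20% and recover 8%.

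Most of this stands, but it leaves gaps. The action table does not specify each participant's highest action. Table D-3 puts stopping for the day and stopping permanently in one grade and mixes them with fluid and vasopressor criteria; protocol version 1 used a different grading. The worst-category table covers all reasons, split only into AE and other. Multiplying back recovers a proportion or a mean, but the planned comparison would still be run inside the subset. Fluid volume has no all-participant version.

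A reader might also infer that the daily reference makes the more toxic arm look milder, or that stepwise worsening goes unseen. Neither follows. A same-day reference validly isolates each day's infusion. Pre-infusion blood pressure and vasopressor dose are summarised for each day, new vasopressor use is anchored to Day 0 status, and lowest MAP and the share of readings below 65 mmHg need no baseline. The participant in step 4 would count as new use. Only the size of the accumulated change is missed.

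Finally, a reader might infer that these items drive DSMB decisions. The weekly report in section 2 names neither subset item, the boundaries in section 10.2 rest on mortality, and section 10.1 bases safety monitoring on the totality of evidence.

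**Conclusion.** The point holds in a limited form and is minor. Two listed between-arm comparisons condition on a post-randomization event and can reverse when the ratio of any-modification rates exceeds the ratio of severe rates, or when the extra fluid recipients receive small volumes. Whether this will happen cannot be judged from the documents, and other assumed rates give no reversal. Two things are missing: a per-participant highest-intensity modification for hypotension over all mITT, and a fluid volume over all mITT, although vasopressor rise in the same list is zero-filled. The daily reference is a sound choice that a Day 0 reference would usefully supplement. The primary safety endpoint and the mortality boundaries are unaffected.

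**What to change.** In SAP section 6.1:

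1. Make the tested modification comparison an ordered, hypotension-related outcome over all aviptadil mITT participants: none, rate decreased, paused, stopped for the day, stopped permanently. Use the section 3 proportional odds model with disease severity. State where an infusion not attempted because of hypotension falls, since the SAP lists it separately.
2. Make the tested fluid comparison the maximum daily volume over all mITT, with 0 mL for non-recipients, by a rank test stratified by disease severity. State how volumes below 500 mL are scored, because the prevalence line counts crystalloid from 500 mL or equivalent colloid.
3. Keep the two subset figures as untested description, printed beside their prevalence.
4. As a supplement, also report MAP fall and vasopressor rise against the Day 0 pre-infusion value. Keep the daily-reference items.

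The cost is SAP wording and table shells. The planned lines already need the same data, so nothing new has to be collected.
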